8.3.8 Transfusions

All transfusions will be listed and summarized using the FAS. The number of transfusion per patients will be summarized by treatment phase and for each cycle.

8.3.9 Hematopoietic stem cell transplantation (HSCT)

Patient moving to HSCT will be reported by treatment phase. HSCT in CR or CRi with adequate blood count recovery and relapse/induction failure will be distinguished in the analysis. HSCT analyses will be based on the FAS.

9 Safety analyses

All safety analyses will be based on the safety set. Safety summaries (tables, figures) include data from the on-treatment period see ([Section 3.5.2](#)). Safety data will be presented in listing for patients who started treatment but were not randomized.

9.1 Deaths

Death summaries for on-treatment, and all (including both on-treatment and post-treatment) fatal cases will be produced by treatment group, SOC and PT. All deaths on safety set will be listed, post treatment deaths will be flagged. Separate listings of deaths prior to randomization will be provided for all screened subjects. Death summaries at day 30 and day 60 after start of treatment will also be summarized by treatment group, age and anthracyclin.

9.2 Adverse events (AEs)

Reporting of AEs

All AEs recorded during the study will be listed and summarized. AEs will be summarized via treatment group by presenting the number and percentage of patients having at least one AE (regardless of study drug treatment in each primary system organ class) and for each preferred term using MedDRA coding (MedDRA version 22.0 or later will be used). A patient with multiple occurrences of an AE will be counted only once in the respective AE category.

AE summaries will be presented by primary system organ class, preferred term, and maximum CTC grade (CTCAE version 5.0 will be used). A patient with multiple CTC grades for an AE category will be summarized under the maximum CTC grade recorded for the event.

AE summaries will include all treatment-emergent AEs starting on or after Study Day 1 (i.e. on or after the day of the first intake of study treatment) and starting no later than 30 days after study treatment discontinuation.

AE summaries

The following incidences of AE summaries will be produced by treatment group:

- AEs regardless of study drug relationship by primary system organ class and preferred term.
- AEs regardless of study drug relationship by primary system organ class and preferred term by age (< 60 vs. => 60 years).
- AEs regardless of study drug relationship by primary system organ class, preferred term and anthracyclin.
- AEs regardless of study drug relationship by primary system organ class, preferred term, anthracyclin and age(<60 vs. >= 60 years)
- AEs with suspected relationship to study drug by primary system organ class and preferred term.
- Deaths by primary system organ class and preferred term.
- Deaths by primary system organ class and preferred term and age (<60 vs. >= 60 years)
- Deaths by primary system organ class and preferred term with Idarubicin /Daunorubicin during Induction
- Deaths by primary system organ class and preferred term and age with Idarubicin /Daunorubicin during Induction (<60 vs. >= 60 years)Deaths by primary system organ class and preferred term after Hematopoietic stem cell transplantation (HSCT)
- SAEs regardless of study drug relationship by primary system organ class and preferred term
- SAEs with suspected relationship to study drug by primary system organ class and preferred term
- Non-SAEs by primary system organ class and preferred term
- SAEs with fatal outcome by primary system organ class and preferred term

- AEs leading to study drug discontinuation, regardless of study drug relationship by primary system organ class and preferred term
- AEs requiring dose adjustment or temporarily study-drug interruption regardless of study drug relationship by primary system organ class and preferred term
- AEs requiring additional therapy regardless of study drug relationship by primary system organ class and preferred term.
- AEs requiring hospitalization regardless of study drug relationship by primary system organ class and preferred term.

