In Study [A2301], the safety profile (overall) for both the midostaurin and placebo groups was consistent. The median duration of exposure to midostaurin and placebo was 42.0 days (range 2-576 days) and 34.0 days (range 1-465 days), respectively. As expected, the most frequent grade 3/4 AEs in both groups were related to myelosuppression (neutropenia, anemia, thrombocytopenia, febrile neutropenia) and occurred in nearly all patients during the induction/consolidation phases. The addition of midostaurin did not prolong the time to platelet or neutrophil recovery in the induction and consolidation phases.

The most frequent non-hematologic grade 3/4 AEs in the midostaurin group were infections (device-related), diarrhea, and exfoliative dermatitis; and for the placebo arm, hypokalemia, diarrhea, and pneumonia. AEs were generally balanced between the two arms, with the exception of exfoliative dermatitis and transaminase elevations, which occurred more

frequently in midostaurin-treated patients. Please refer to the Investigators Brochure for additional information.

2 Rationale

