2.2.2.1 Safety and tolerability of midostaurin post-consolidation therapy

When the post-consolidation phase (single agent midostaurin or placebo) was assessed separately, a difference in the type and severity of adverse drug reactions (ADRs) was observed compared to the phases of combined treatment with chemotherapy i.e. induction and consolidation phase. The overall incidence of ADRs during the post-consolidation phase was generally lower. ADR during the post-consolidation phase with at least $\geq 5\%$ difference between the midostaurin and placebo arms were: nausea (46.4% vs 17.9%), hyperglycaemia (20.2% vs 12.5%), vomiting (19% vs 5.4%) and lymphopenia (16.7% vs 8.9%). Most of the hematological abnormalities reported occurred during the induction and consolidation phase when the patients received midostaurin or placebo in combination with chemotherapy. The most frequent grade 3/4 hematological abnormalities reported in patients during the post-consolidation phase with midostaurin and placebo respectively were absolute neutrophil count decrease (20.8% vs 18.9%) and leukopenia (7.5% vs 5.9%). Overall, ADRs reported during the post-consolidation phase were of mild to moderate intensity and led to very few discontinuations (8.1% for midostaurin arm and 5.4% for placebo arm). The median duration of exposure in the post-consolidation phase was the same in both treatment groups (336 days) [Study A2301-Table 12-2], demonstrating the tolerability of midostaurin monotherapy following chemotherapy for previously untreated AML.

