To compare the time to platelet recovery in the two treatment groups.	Number of days from the first day of a chemotherapy cycle to first day platelets $\geq 50 \times 10^9/L$. Number of days from day 1 of commencing induction therapy to first day platelets $\geq 100 \times 10^9/L$.
To assess the safety and tolerability of midostaurin in combination with chemotherapy and as monotherapy during post-consolidation.	Frequency/severity of AEs, and laboratory abnormalities.
To further characterize the pharmacokinetics of midostaurin, CGP52421 and CGP62221.	Plasma concentrations and pharmacokinetic parameters for midostaurin, CGP52421 and CGP62221.
To assess the impact of midostaurin on health related quality of life and AML symptom reduction.	Change from baseline score for each time point for the FACT-Leu and the EQ5D-5L (visual analogue scale (VAS)) by treatment arm.

[REDACTED]

[REDACTED]

[REDACTED]

[REDACTED]

[REDACTED]

[REDACTED]

[REDACTED]

[REDACTED]

[REDACTED]

[REDACTED]

[REDACTED]

[REDACTED]

[REDACTED]

Data analysis general information

The statistical analysis of this study will be performed by Novartis. SAS® version 9.4 or later (SAS Institute Inc., Cary, NC, USA) will be used for all analyses. All data are part of the Clinical Database and will be exported to SAS® files for analysis. EAST version 6.4 or later (Cytel Inc.®) will be used to determine stopping boundaries in the group sequential plan.

The final EFS analysis was supposed to be performed by Novartis. However, since the study was stopped at first interim analysis only an updated EFS analysis will be provided in the final CSR. The first interim analysis of EFS was performed by an independent external statistician and an independent external programmer (CRO not involved with the conduct of the study). The study was stopped at this first interim and no further analyses are to be performed (i.e. study stopped).

The study will end when the last ongoing patient will have completed or discontinued treatment.

All events with start date before or on the cut-off date and end date after the cut-off date will be reported as 'ongoing'. The same rule will be applied to events starting before or on the cut-off date and not having documented end date. This approach applies, in particular, to adverse event and concomitant medication reports. For these events, the end date will not be imputed and therefore will not appear in the listings.

General analysis conventions

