3.6.2 On-treatment assessment/event

All on-treatment assessments/events are any assessments/events obtained in the time interval:

[Date of first administration of study treatment; date of last administration of study treatment +30 days], i.e., inclusive lower and upper limit.

The calculation of study treatment duration may use different rules as specified in [Section 6.1](#).

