9.3 Laboratory data

On analyzing laboratory assessments, data from all sources (central and local laboratories) will be combined. The summaries will include on-treatment laboratory assessments.

The following summaries will be produced for the laboratory data (by laboratory parameter):

- Shift tables using CTC grades to compare baseline to the worst post-baseline value will be produced for hematology and biochemistry laboratory parameters with CTC grades.

For laboratory parameters where CTC grades are not defined.

- Shift tables to the worst post-baseline value will be produced using the low/normal/high classifications based on laboratory reference ranges.

Liver function parameters

Liver function parameters of interest are total bilirubin (TBIL), Alanine transaminase (ALT) and enzymes aspartate transaminase (AST). The number (%) of patients with worst post-baseline values as per Novartis Liver Toxicity guidelines will be summarized:

- ALT or AST > 3xULN
- ALT or AST > 5xULN
- ALT or AST > 8xULN
- ALT or AST > 10xULN
- ALT or AST > 20xULN
- TBIL > 2xULN
- TBIL > 3xULN
- ALT or AST > 3xULN & TBIL > 2xULN

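### The safety objective names midostaurin monotherapy in post-consolidation, but no AE, laboratory, QTc or vital-sign summary in SAP 9.2–9.5 is split by treatment phase

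*SAP*

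**What the plan says.** The objectives table in SAP section 2 gives the safety objective as "To assess the safety and tolerability of midostaurin in combination with chemotherapy and as monotherapy during post-consolidation". Protocol Table 3-1 has the same objective. The endpoint attached to it is "Frequency/severity of AEs, and laboratory abnormalities", with no phase stated.

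The opening of SAP section 9 bases all safety analyses on the safety set and draws the summaries from the on-treatment period. SAP 3.6.2 defines that period as one interval: "Date of first administration of study treatment; date of last administration of study treatment +30 days], i.e., inclusive lower and upper limit". Study treatment includes the chemotherapy, so the interval opens on Day 1 of induction.

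Within that interval:

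- **AEs (SAP 9.2).** "A patient with multiple occurrences of an AE will be counted only once in the respective AE category", and a patient with several grades is shown at the maximum. The listed tables are by treatment group, some also by study-drug relationship, age or anthracycline. None is by phase.
- **AESIs (SAP 9.2.1).** Patients with at least one event, with no phase.
- **Laboratory (SAP 9.3).** "Shift tables using CTC grades to compare baseline to the worst post-baseline value will be produced", with a baseline taken at or before the start of study treatment (SAP 3.6.1).
- **QTc and vital signs (SAP 9.4, 9.5).** Notable values, with no phase.

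The subgroup list in SAP 3.8.5 does not include phase. Protocol 10.5.3 also has a single on-treatment period.

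**The concern.** An objective with two named parts should have at least one planned summary for each. Here the stated endpoint, AE frequency and severity plus laboratory abnormalities, has no summary for the monotherapy part.

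Pooling makes this more than a matter of layout. A patient with nausea in induction and again in post-consolidation appears once, at the worse grade, and the table does not show in which phase. The laboratory shift takes the worst value after a pre-chemotherapy baseline. Protocol 1.2.1.2 says that grade 3/4 myelosuppression in A2301 "occurred in nearly all patients during the" induction and consolidation phases, so a later cytopenia at or below that grade would leave no trace. The denominator also includes every patient who never reached post-consolidation.

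The protocol itself treats the phases as different. Section 2.2.2.1 says of A2301: "When the post-consolidation phase (single agent midostaurin or placebo) was assessed separately, a difference in the type and severity" of adverse drug reactions was seen compared with the chemotherapy phases. Section 2.8 expects mainly grade 1 or 2 gastrointestinal events to be more frequent than on placebo in post-consolidation. No planned table can check that expectation.

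**Working it through.** **Step 1: text check.** There is no sample-size or power figure to reproduce. Reading SAP 9.1–9.5 and Protocol 10.5.3 for any split by phase gives:

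- AE, SAE, AESI, laboratory, QTc and vital-sign summaries by phase: none.
- Safety output not pooled over all phases: deaths at day 30 and day 60 (SAP 9.1), and deaths after HSCT (SAP 9.2).
- Related output by phase: primary reason for discontinuation (SAP 4.5), relative dose intensity (6.7.3.2), MRD (8.3.6.1) and transfusions (8.3.8).

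A split by phase is therefore feasible with the data structure already in use.

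**Step 2: how far pooling can dilute a difference (illustration only).** Let c be the share of patients in each arm with the event during chemotherapy, f the share who reach post-consolidation, and m the incidence in that phase. With the phases independent and c and f equal in both arms:

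- pooled incidence = 1 − (1 − c)(1 − f·m)
- pooled difference = (1 − c) × f × (m on midostaurin − m on placebo)

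Inputs:

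- m for nausea is 46.4% v 17.9%, a difference of 28.5 points (Protocol 2.2.2.1). It is read as a share of patients entering the phase; the protocol does not state the denominator.
- f = 205/717 = 28.6% (Protocol 2.2.2 and 1.2.1.2), with 50% as an alternative assumption.
- c is not given in either document and is assumed, from 30% to 90%.

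Example: (1 − 0.8) × 0.286 × 28.5 = 1.6 points.

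| Assumed c | f = 28.6% | f = 50% |
|---|---|---|
| 30% | 5.7 | 10.0 |
| 60% | 3.3 | 5.7 |
| 80% | 1.6 | 2.85 |
| 90% | 0.8 | 1.4 |

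For vomiting (19% v 5.4%, 13.6 points), the same formula gives 2.7 down to 0.4 points at f = 28.6%, and 4.8 down to 0.7 at f = 50%.

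**Step 3: unequal entry.** The 205 were 120 on midostaurin and 85 on placebo. Assuming about 358 randomised per arm (717/2), the shares are 33.5% and 23.7%. At c = 80% the nausea difference is 0.2 × (33.5 × 0.464 − 23.7 × 0.179) = 0.2 × (15.5 − 4.2) = 2.3 points, against 1.6 with a common share. For c from 60% to 90% it runs from 4.5 to 1.1 points, inside the range above.

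**The case against.** The strongest case on the other side has four parts.

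1. **The information exists.** SAP 4.5 tabulates discontinuation reasons for each phase, SAP 6.7.3.2 gives relative dose intensity by phase, and all AEs are listed. AEs suspected to be related to study drug have their own tables, and SAP 3.2 defines study drug as midostaurin or placebo alone. Protocol 8.1.1 collects AE start dates and a new entry on worsening. This stands: what is missing is a presentation, not data. But listings give no incidence by arm, and a primary discontinuation reason gives no AE term or grade.

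2. **The trial stopped for futility.** SAP section 1 says that analyses were reduced, that the study was unblinded and that most patients left within weeks. SAP 8.3.6.1 makes its own post-consolidation MRD comparison conditional on sufficient numbers. This stands as a reason for a short descriptive set, and against exposure-adjusted rates or a split by HSCT. It does not explain silence: the SAP keeps the objective, adds safety tables by anthracycline, and in section 11 reports no change from the protocol-specified analysis.

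3. **The pooled comparison is the one that randomisation protects, and it follows the protocol.** True, and it should stay.

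4. **There may be little to mask.** In A2301, post-consolidation grade 3/4 neutrophil decrease was 20.8% v 18.9% and leukopenia 7.5% v 5.9%. Discontinuations because of drug reactions were 8.1% v 5.4%, and median exposure was equal at 336 days. Nausea is the largest difference reported. This limits the size of the point but does not remove the gap.

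**Conclusion.** The point holds as an omission in the planned tables. Followed as written, SAP 9.2–9.5 yields no frequency or severity of AEs or laboratory abnormalities by arm under monotherapy, although the objective asks for it. The pooled tables can understate a difference in that phase. The illustrative shrinkage, from 28.5 to roughly 1–10 points, rests on an assumed chemotherapy-phase incidence, an assumed share reaching the phase, and independence between phases.

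A reader might infer more than this, and the documents do not support it:

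- **That every safety table is pooled.** The day-30, day-60 and post-HSCT death summaries are not.
- **That the monotherapy question cannot be answered.** The partial outputs and dated AE records say otherwise.
- **That no later event can count.** A new term still enters the incidence tables, and a higher grade still moves the maximum.
- **That A2301 showed a monotherapy signal only when the phase was taken alone.** Protocol 2.2.2.1 contrasts phases at that point and does not say only. Section 1.2.1.2 reports differences between arms in the overall profile, for exfoliative dermatitis and transaminase elevations.
- **That pooled arms would look near-equal.** This depends on a chemotherapy-phase nausea rate that neither document gives. The phrase about nearly all patients concerns myelosuppression, not gastrointestinal events.

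Severity is moderate. It is a cheap improvement, not a defect that undermines the report.

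**What to change.** In SAP 9.2–9.3, add descriptive tables by arm for post-consolidation: AEs of any grade and of grade 3/4, SAEs, AESIs, AEs leading to study-drug discontinuation, and laboratory shifts.

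- **Patients:** those with at least one post-consolidation dose.
- **Events:** those starting or worsening from post-consolidation Cycle 1 Day 1 to 30 days after the last dose.
- **Laboratory baseline:** the last value before that Day 1.
- **Label:** descriptive, in a selected subset not protected by randomisation and partly observed after unblinding.

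Keep the pooled tables unchanged.

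The cost is SAP wording and one extra table set from data already collected with dates. The downside is small numbers and the risk of over-reading a selected comparison, which the label is there to limit. If the sponsor judges the numbers too small, the SAP should at least say that the monotherapy part will be covered by listings only.

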4.1 Description of study design

This is a randomized, double-blind, multi-center, placebo-controlled phase III study of midostaurin (PKC412) or placebo in combination with idarubicin/daunorubicin and cytarabine for induction therapy, intermediate-dose cytarabine for consolidation therapy, followed by post-consolidation therapy with midostaurin or placebo in adult patients with newly diagnosed FLT3-MN (SR<0.05) AML, i.e., FLT3 mutant to wild type signal ratio below the 0.05 clinical cut-off. The study is designed to evaluate the efficacy and safety of midostaurin combined with intensive chemotherapy in this indication. 502 adult patients with newly diagnosed AML demonstrating FLT3-MN (SR<0.05) as determined by a Novartis designated laboratory will be enrolled at approximately 150-180 sites worldwide.

Figure 4-1 Study Design

Eligible and consented patients are allowed to start with the 7+3 chemotherapy immediately after the unequivocal diagnosis of AML; the day of the first dose of chemotherapy is defined as Day 1.

Patients will be tested for the absence of FLT3-ITD and FLT-TKD mutations, using a validated clinical trial assay in a Novartis designated laboratory. Absence of mutation is defined as ITD and TKD activating mutations at codons D835 and I836 in the FLT3 gene, below the clinical cutoff of 0.05 mutant to wild type signal ratio.

Patients with confirmed FLT3-MN (SR<0.05) AML will be randomly assigned 1:1 to midostaurin or placebo by using a stratified randomization according to age (<60 vs. ≥60 years), Patients will be randomized on Day 8, i.e., the day of the first dose of midostaurin or placebo. Patients with a FLT3 mutation or with an unknown FLT3 mutation status by study Day 8 will be considered as molecular screening failures and cannot be randomized.

Provided that FLT3-MN (SR<0.05) status has been confirmed, patients meeting all other eligibility criteria will start the administration of midostaurin or placebo on Day 8.

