7.1.3 Treatment period

Patients will be assigned on Cycle 1 Day 8 of induction therapy to midostaurin or placebo using a stratified randomization according to age.

- Study treatment will begin on Day 1 of Cycle 1 with chemotherapy: daunorubicin from Day 1 to Day 3 and cytarabine from Day 1 to Day 7. Study treatment will continue on Day 8 with midostaurin/placebo until 48 hours prior to start of next cycle.
- Chemotherapy and midostaurin/placebo will be administered as indicated in [Table 7-1](#) and until the subject experiences any of the following: persistent disease, relapse as determined by investigator, unacceptable toxicity that precludes further treatment, pregnancy, start of non-protocol anti-cancer therapy, discontinuation at the discretion of the Investigator or patient, loss to follow-up, death, or study termination by the Sponsor.

Visit frequency

- Induction phase cycle 1: most assessments will be scheduled once or twice per week until hematology recovery. This cycle may be longer than 28 days (until hematology recovery occurs), and the assessments will be performed accordingly but cannot be longer than 43 days (28 days plus up to 14 additional days for blood count recovery) in total. If the patient has evidence of persistent leukemia on a bone marrow evaluation at the end of the first induction cycle, then a second cycle of induction therapy will be administered.
- Induction phase cycle 2: assessments will be the same as for Cycle 1, except for the PK [REDACTED] and study drug dispensation. The maximum length of induction cycle 2 is 50 days (28 days plus up to 21 additional days for blood count recovery). For details of assessments in induction Cycles 1 and 2, refer to [Table 7-1](#).
- Patients who achieve a CR or CRi with adequate blood count recovery will continue with consolidation therapy for 3 to 4 cycles with a maximum length of 50 days (28 days plus up to 21 additional days for blood count recovery) each. Patients achieving CR/CRi with adequate blood count recovery after induction cycle 1 will have 4 cycles of consolidation therapy and patients achieving CR or CRi with adequate blood count recovery after the second cycle of Induction will have 3 cycles of consolidation therapy.

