3.2 Study drug and study treatment

Study drug refers to Midostaurin (PKC412) or Placebo (PBO).

Study treatment refers to

- Midostaurin + Chemotherapy (idarubicin/daunorubicin, cytarabine) or
- Placebo + Chemotherapy (idarubicin/daunorubicin, cytarabine) (control group).

Study treatment components refer to

- Midostaurin/Placebo or
- Idarubicin/Daunorubicin or
- Cytarabine

Study drug combination partner refers to Idarubicin/Daunorubicin or Cytarabine

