3.5 Date of first administration of study treatment

The date of first administration of study treatment is derived as the first date when a non-zero dose of any component of study treatment was administered and recorded on the exposure eCRF. For example, if the 1st dose of study drug A is administered on 04Jan2019, and the 1st dose of its combination partner, drug B, is administered on 03Jan2019, the date of the first administration of study treatment is on 03Jan2019). The date of the first administration of study treatment will also be referred as the *start of study treatment*.

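### By-arm AE tables start at chemotherapy Day 1, seven days before randomization, so pre-assignment events attenuate the all-cause comparison of midostaurin with placebo

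*SAP*

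**What the plan says.** SAP 9.2 sets the counting window: "AE summaries will include all treatment-emergent AEs starting on or after Study Day 1", which it explains as "on or after the day of the first intake of study treatment". SAP 3.5 defines the start of study treatment as the "first date when a non-zero dose of any component of study treatment was administered", and SAP 3.2 includes idarubicin/daunorubicin and cytarabine among those components. Study drug, by contrast, means midostaurin or placebo alone. SAP 3.6.2 uses the same anchor for the on-treatment interval: "Date of first administration of study treatment; date of last administration of study treatment +30 days".

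Protocol 4.1 says that "the day of the first dose of chemotherapy is defined as Day 1". Protocol 7.1.3 says "Patients will be assigned on Cycle 1 Day 8 of induction therapy to midostaurin or placebo", and Protocol 4.1 and 6.1 put the first midostaurin or placebo dose on that same day.

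The counting rule in SAP 9.2 is: "A patient with multiple occurrences of an AE will be counted only once in the respective AE category". Where a patient has several grades for a category, only the maximum is tabulated. AE summaries are produced by treatment group on the Safety Set, which requires randomization and at least one dose of midostaurin or placebo (SAP 3.8.2). No AE table in SAP 9.2 or 9.2.1 starts at the first study-drug dose, and none is split by treatment phase.

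**The concern.** The first week of intensive induction chemotherapy is finished before any arm exists. Events that start in that week cannot be caused by the assigned drug, yet for randomized patients they enter the tables that set the two arms side by side. Because a patient counts once per term, an early event also takes the place that a later event of the same term on study drug would have filled.

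What is at stake is how readable the all-cause safety comparison is for the added drug. Protocol 2.8 itself names the separation of chemotherapy toxicity from midostaurin toxicity as the main difficulty. The earlier phase III trial, as summarized in Protocol 1.2.1.2, showed mostly similar AE frequencies in the two arms when the drug was combined with chemotherapy. Protocol 2.2.2.1 reports clear differences in nausea and vomiting when the post-consolidation phase was looked at separately. Randomization on Day 8 offers a clean starting point, and the planned tables do not use it.

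**Working it through.** The plan gives no power, margin or expected AE rate for the arm comparison, so there is no figure of its own to reproduce. The check is of dates, counting rules and simple arithmetic.

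**1. Dates.** Day 8 - Day 1 = 7 days. This matches the 168-hour cytarabine infusion in Protocol 6.1.1.1 (168/24 = 7).

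**2. Does anything remove these events?** The Safety Set selects patients but keeps their Day 1-7 events. SAP 3.8.2 and the opening of SAP 9 separate pre-randomization data only for patients who were never randomized. Protocol 10.5.3.1 starts the on-treatment period at the first dose of study medication, a term it does not restrict to midostaurin or placebo.

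**3. How the counting rules act.** Take a patient with an event on Day 3 and the same term on Day 12:
- Grade 1, then grade 1: nothing is added to any table.
- Grade 1, then grade 3: the any-grade count is unchanged, but the maximum-grade table shows grade 3.
- Grade 3, then grade 3: nothing is added to any table.

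**4. Size.** Let q be the share of patients with the term in Days 1-7, equal in both arms in expectation. Let RD0 and RD1 be the post-Day-8 risk differences among patients without and with such an early event.
- Post-randomization difference: (1-q)·RD0 + q·RD1
- Difference shown in a from-Day-1, any-grade table: (1-q)·RD0
- Part lost: q·RD1

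If post-Day-8 risks do not depend on early events, then RD0 = RD1 = RD, tabulated incidence is q + (1-q)p, and the table shows (1-q)·RD.

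The documents do not give q. With an assumed range and assumed post-Day-8 risks of 40% and 20%:

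| q | midostaurin | placebo | difference |
|---|---|---|---|
| 0 | 40% | 20% | 20 points |
| 10% | 46% | 28% | 18 points |
| 30% | 58% | 44% | 14 points |
| 50% | 70% | 60% | 10 points |
| 70% | 82% | 76% | 6 points |

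For scale only, Protocol 2.2.2.1 gives post-consolidation rates from the earlier trial. Nausea was 46.4% vs 17.9%, a difference of 28.5 points. Multiplied by (1-q) for q = 10%, 30%, 50% and 70%, this becomes 25.65, 19.95, 14.25 and 8.55 points. Those rates come from a phase without chemotherapy and are not a forecast for this trial.

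**5. Which tables.** Affected: the all-cause AE, SAE and AESI summaries, and the maximum-grade tables in the limited way shown in step 3. Largely unaffected: AEs suspected to be related to study drug, and AEs leading to study-drug discontinuation or interruption, because study drug means midostaurin or placebo. For the relationship tables this rests on attribution being recorded separately for midostaurin/placebo. Protocol 8.2.2 requires that for SAEs, whereas Protocol 8.1.1 asks only for relationship to study treatment. Safety Set deaths cannot fall before Day 8, because a study-drug dose is required.

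**The case against.** The Day 1 anchor is a consistent definition and not a slip. Both documents define study treatment as the whole regimen, and the safety objective covers midostaurin in combination with chemotherapy. The tabulated difference is a valid estimate of the difference in cumulative incidence from Day 1; it is attenuated only against a different target, incidence from Day 8. This stands, and it is why the existing tables should be kept.

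A reader might infer that the tables are biased in favour of midostaurin. The documents do not support that: the early events precede assignment and fall equally on both arms in expectation. A reader might also infer that a patient with early nausea can never register nausea on study drug. That holds only for any-grade counts. Protocol 8.1.1 has a worsened event entered again with its own start date, so a later, higher grade still reaches the maximum-grade tables.

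The reach of a change is limited. With the earlier trial's median exposures (Protocol 1.2.1.2) plus 30 days, the week is 7/(7+34+30) = 9.9% or 7/(7+42+30) = 8.9% of the on-treatment window. Later chemotherapy toxicity still enters both arms, so cytopenia tables could stay near ceiling, and a Day 8 start does not isolate post-consolidation. This also stands. But the share of the window is not q: that week is the first block of intensive chemotherapy, and q for common chemotherapy AEs could differ widely from 9-10%.

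Finally, the trial stopped for futility and the SAP describes a reduced report. That lowers the stakes without changing what the tables show.

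**Conclusion.** The point holds as one of attenuation. By-arm AE counting starts seven days before randomization, and once-per-patient counting lets a Day 1-7 event absorb a later one. The any-grade, all-cause AE, SAE and AESI tables therefore understate the between-arm difference relative to post-randomization incidence wherever early events are common and midostaurin also raises the risk in patients who had them. The maximum-grade tables are affected only when the later grade does not exceed the earlier maximum.

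The size cannot be fixed from the documents. The 18-to-6-point range for a 20-point difference rests on an assumed q of 10-70% and on post-Day-8 risks that do not depend on early events. For rare or late AEs, q and hence the loss are likely to be small. The plan specifies no test for the AE comparison, so no power statement follows. Nor do the documents support reading the from-Day-1 tables as wrong: they answer a regimen-level question.

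**What to change.** Keep the from-Day-1 tables as the description of the regimen. Add by-arm all-cause AE, SAE, maximum-grade and AESI tables restricted to AEs that start or worsen on or after the first midostaurin or placebo dose, a date already derived under SAP 3.3. Three details need to be written down:

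- Judge worsening against the patient's status just before that dose. The safety baseline in SAP 3.6.1 is tied to the start of study treatment and does not serve this purpose.
- Exclude entries that only record improvement. Under Protocol 8.1.1, a grade 3 or 4 event that improves gets a new entry with a new start date, so a Day 5 event that improves on Day 10 would otherwise look like a new event.
- Show Day 1-7 events of randomized patients in a separate table.

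Use the added tables for the between-arm safety comparison. Label them as added after unblinding, since SAP section 1 states that decisions on the final analysis were made after the study data were unblinded.

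The cost is one extra flag and a second set of tables. First-week chemotherapy events leave the comparison tables but remain in the regimen tables and the separate Day 1-7 table.
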